1.0 Introduction and Background

Radiation-induced Skin Reactions in Head and Neck Cancer

Radiotherapy (RT) is an effective intervention for treating head and neck cancer. The primary mechanism of action of RT is to create enough DNA damage within each tumor cell to prevent replication and ultimately induce programmed cell death. This mechanism extends beyond the targeted tumor to normal surrounding tissue. This field effect can be visualized by the effect of RT on the skin within a treatment portal. Approximately 85% of patients undergoing RT experience a moderate-to-severe skin reaction (1), the severity of which can be graded using various scales such as the RTOG toxicity criteria (2) and the National Cancer Institute (NCI) Common Terminology Criteria for Adverse Events (CTCAE) version 5 (3). The disturbance of the cutaneous barrier function can significantly impact both health-related quality of life and the course of treatment (4). If the skin reaction is severe enough, a treatment break may be recommended (5). Managing the symptoms associated with skin reactions is important for ensuring completion of RT in a timely manner and increasing patient self-esteem (4). Current skin care recommendations typically include the use of non-fragrant, hypo-allergenic moisturizers (4). Further investigations of topical agents to reduce the symptomatic impact of radiation-induced skin reaction are needed.

KeraStat Cream for Radiation-induced Skin Reactions

KeraStat Cream is a non-sterile, non-implantable, emulsion-based wound dressing intended to act as a protective covering in the management of a variety of minor skin wounds and first and second degree (partial thickness) burns as well as skin undergoing radiation treatment. KeraStat Cream uses human hair-derived keratin proteins and is applied topically to the wound surface to absorb exudate, provide a moist environment, and create an environmental barrier supportive of healing. This cream has recently been studied in the breast cancer patient population undergoing radiotherapy to the breast but has not yet been investigated in patients with head and neck cancer being treated with definitive RT.

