The investigators have demonstrated the feasibility of KeraStat cream during breast RT for patients with breast cancer [data not published]. This study represents a subsequent step to confirm the feasibility of extending comparative studies of KeraStat cream versus routine skin care to patients with a different primary cancer site (head and neck cancer). Due to significant differences in the nature of the head and neck cancer treatment, including the higher risk of high-grade radiation dermatitis experienced by head and neck cancer patients, it is first necessary to confirm the feasibility and tolerability of KeraStat cream in these patients. These data would then directly inform randomized, comparative studies to evaluate the efficacy of KeraStat cream to reduce radiation dermatitis for patients receiving head and neck RT.

KeraNetics has determined that this study is a non-significant risk study under 21 CFR 812.3(m). This device is not intended as an implant. It is not for use supporting or sustaining human life. It is not for a use of substantial importance in diagnosing, curing, mitigating, or treating disease or otherwise preventing impairment of human health, and it does not

otherwise present a serious risk to health, safety, or welfare of a subject. Furthermore, KeraStat® Cream is classified as a wound dressing; wound dressings are classified as nonsignificant risk devices in FDA's "Information Sheet Guidance for IRBs, Clinical Investigators, and Sponsors: Significant Risk and Nonsignificant Risk Medical Device Studies" published January 2006.

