2.0 Objectives

This is a single site, randomized, open-label comparison pilot study to assess the feasibility and effectiveness of KeraStat Cream compared with routine skin care (RSC) in managing RT-induced early adverse skin reaction (EASR) in patients undergoing RT to the head and/or neck.

Hypothesis: The use of KeraStat Cream in patients receiving radiotherapy for head and neck is feasible, tolerable, and reduces the severity of EASR in the treated region of interest.

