2.2 Secondary Objective(s)

- 2.2.1 To determine the tolerability of KeraStat Cream in patients receiving radiotherapy for head and neck cancer compared to routine skin care.
- 2.2.2 To assess the effectiveness of KeraStat Cream in reducing the severity of EASR in patients receiving radiotherapy for head and neck cancer, compared to routine skin care. This will be performed by evaluating:
 - 2.2.2.1 Objective evaluation of EASR using the CTCAE Version 5.0 scale of radiation dermatitis,
 - 2.2.2.2 Patient-reported outcomes of radiation dermatitis using the PRO-CTCAE version 1.0, and
 - 2.2.2.3 Dermatologic-specific quality of life assessment
- 2.2.3 To estimate the amount of KeraStat Cream used per patient and coverage on the skin.

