5.2 Secondary Outcomes

5.2.1 Tolerability is measured by the number of patients who discontinue skin care regimen due to intolerance for any reason.

^{*}Protocol Registration is open from 8:30 AM - 4:00 PM, Monday-Friday.

- 5.2.2 The effectiveness of KeraStat Cream in reducing EASR will be assessed as follows:
 - 5.2.2.1 Objective assessment of EASR, defined as Grade 2+ using the CTCAE version 5.0 scale of radiation dermatitis (Appendix H)
 - 5.2.2.2 Patient-reported assessment of skin toxicity using the PRO-CTCAE version 1.0 scale of radiation skin reaction (Appendix H)
 - 5.2.2.3 Dermatologic-specific quality of life will be measured using the Dermatology Life Quality Index (Appendix I)
- 5.2.3 Skin coverage by the will be calculated the number of tubes of KeraStat Cream used.

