11.2 Analysis of Secondary Objective

- 11.2.1 The rate of discontinuation for any reason will be used as a measure of tolerability, with patients who do not discontinue the skin care regimen being classified as tolerant. In each arm, a 95% confidence interval will be calculated around the estimate of tolerability.
- 11.2.2 Proportion of EASR (CTCAE v5.0 Grade 2+ radiation dermatitis) will be compared between the KeraStat group and the RSC group at the end of treatment, using a Fisher's exact test.
- 11.2.3 Mean scores of the modified PRO-CTCAE patient-reported outcome scales collected each week over the 6-7 weeks of radiation therapy and at the onemonth post treatment follow-up visit will be compared between the KeraStat and RSC groups using a simple repeated measures analysis of variance model with treatment group as the independent variable of interest.
- 11.2.4 Mean DLQI score at each time point will be compared between the KeraStat and RSC groups, again using a simple repeated measures analysis of variance model with treatment group as the key independent variable. Additionally, the mean of the highest DLQI score across all time points will be compared between the KeraStat and RSC groups using a t-test.
- 11.2.5 Skin coverage (calculated as number of tubes of KeraStat Cream used per week) will be summarized with a frequency distribution and computation of central tendency and variability (mean, median, and standard deviation).

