Appendix H - Toxicity Assessment Form

- · ·					
	r: PID:				
PI://// Date (mm/dd/yy): ///					
To be complete	ted by research nurse:				
Name of Pers	on Completing Form:				
Time Point (se	elect one where applicable):				
Baseline (F	Pre-RT)				
Week 1	☐ Week 2 ☐ Week 3 ☐ Week 4				
☐ Week 5	☐ Week 6 ☐ Week 7 ☐ Week 8 ☐ Week 9				
1-month P	ost-RT Follow-up				
To be complet	ted by research nurse and confirmed by treating radiation	oncologist:			
Radiation De	rmatitis Scale				
CTCAE Version 5.0 Grade	Definition	Present (Check one that best applies)			
0	None				
1	Faint erythema or dry desquamation				
2	Moderate to brisk erythema; patchy moist desquamation, mostly confined to skin folds and creases; moderate edema				
3	Moist Desquamation in areas other than skin folds and creases; bleeding induced by minor trauma or abrasion				
4	Life-threatening consequences; skin necrosis or ulceration of full thickness dermis; spontaneous bleeding from involved site; skin graft indicated				
5	Death				
	Oral Mucositis Scale				
CTCAE Version	Definition	Present (Check one			

5.0 Grade		that best applies)
0	None	
1	Asymptomatic or mild symptoms; intervention not indicated	
2	Moderate pain or ulcer that does not interfere with oral intake; modified diet indicated	
3	Severe pain; interfering with oral intake	
4	Life-threatening consequences; urgent intervention indicated	
5	Death	

PRO-CTCAE Symptom Assessment

To be completed by the patient.

25. PRO-CTCAE™ Symptom Term: Skin dryness						
a. In the last 7 days, what was the SEVERITY of your DRY SKIN at its WORST?						
O None O Mild O Moderate O Severe O Very severe						

28. PRO-CTCAE™ Symptom Term: Itching						
a. In the last 7 days, what was the SEVERITY of your ITCHY SKIN at its WORST?						
O None O Mild O Moderate O Severe O Very severe						

36. PRO-CTCAE™ Symptom Term: Radiation skin reaction						
a. In the last 7 days, what was the SEVERITY of your SKIN BURNS FROM RADIATION at their WORST?						
O None O Mild O Moderate O Severe O Very severe O Not applicable						

37. PRO-CTCAE™ Symptom Term: Skin darkening				
a. In the last 7 days, did you have any UNUSUAL DARKENING OF THE SKIN?				
O Yes O No				

3. PRO-CTCAE™ Symptom Term: Mouth/throat sores							
a. In the last 7 days, what was the SEVERITY of your MOUTH OR THROAT SORES at their WORST?							
O None	O None O Mild O Moderate O Severe O Very severe						

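### The clinician-graded part of the severity objective is analysed only as CTCAE Grade 2+ yes/no, so a shift from Grade 3 to Grade 2 cannot register

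*Combined protocol and SAP*

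**What the plan says.** The hypothesis in section 2.0 is that the cream "reduces the severity of EASR in the treated region of interest". Secondary objective 2.2.2 is "To assess the effectiveness of KeraStat Cream in reducing the severity of EASR", to be judged through three components: clinician-graded CTCAE, patient-reported PRO-CTCAE, and dermatologic quality of life.

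For the clinician-graded component, section 5.2.2.1 gives the outcome as "Objective assessment of EASR, defined as Grade 2+ using the CTCAE version 5.0 scale of radiation dermatitis". Section 11.2.2 matches it: "Proportion of EASR (CTCAE v5.0 Grade 2+ radiation dermatitis) will be compared between the KeraStat group and the RSC group". The same sentence sets the time point as the end of treatment and the test as Fisher's exact test.

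The data are finer than this. Appendix H has one box per grade from 0 to 5. Grade 2 covers patchy moist desquamation mostly confined to folds, and Grade 3 is "Moist Desquamation in areas other than skin folds and creases; bleeding induced by minor trauma or abrasion". The calendar in section 7.2 schedules the form before RT, weekly during RT and at the 1-month visit.

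The other two components keep their scale. Section 11.2.3 compares mean PRO-CTCAE scores over the weekly and 1-month visits; one item on the form asks "what was the SEVERITY of your SKIN BURNS FROM RADIATION at their WORST". Section 11.2.4 compares mean DLQI at each time point and the highest DLQI score.

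**The concern.** The objective asks how severe the reaction is. The clinician-graded analysis asks only whether it reached Grade 2. A cream that turned Grade 3 reactions into Grade 2 reactions would meet the stated hypothesis and leave the planned result unchanged.

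The protocol's own rationale sits at the upper end of the scale. Section 1.0 says "If the skin reaction is severe enough, a treatment break may be recommended". The Study Rationale explains why head and neck patients need a separate study, "including the higher risk of high-grade radiation dermatitis experienced by head and neck cancer patients", and says the data should inform later randomized comparisons. Planning those will need the grade distribution by arm, which section 11 does not list among its outputs. The trial is open-label, so the patient-reported scales do not fully replace the clinician's grade.

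A smaller point is that 11.2.2 does not tie the end of treatment to a visit in section 7.2.

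**Working it through.** **Inputs.** 12 per arm (section 11.3). Two-sided 5% is assumed, since the plan states no level for this test. All grade distributions below are assumptions.

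**The plan's own figure.** The only sample-size figure is the maximum 95% interval width of 0.578 for compliance. The exact (Clopper-Pearson) interval for 6/12 is 0.211 to 0.789, a width of 0.578, so it reproduces. No figure is given for the dermatitis comparison.

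**Step 1: the structural point, which needs no assumed rates.** The Grade 2+ count is the sum of Grades 2, 3, 4 and 5. Moving a patient from Grade 3 to Grade 2 leaves that sum unchanged. In the extreme, with 12/12 controls at Grade 3 and 12/12 KeraStat patients at Grade 2, the table is 12/12 v 12/12 and Fisher p = 1.0.

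**Step 2: a less extreme example.** Grades 1/2/3 are 2/5/5 in one arm and 2/9/1 in the other.
- Grade 2+: 10/12 v 10/12, difference 0 (Newcombe 95% CI -31 to 31 points), Fisher p = 1.0.
- Grade 3: 5/12 v 1/12, difference 0.417 - 0.083 = 0.333. The Wilson limits are 0.193 to 0.680 and 0.015 to 0.354.
  - Lower limit: 0.333 - √[(0.417 - 0.193)² + (0.354 - 0.083)²] = -0.02.
  - Upper limit: 0.333 + √[(0.680 - 0.417)² + (0.083 - 0.015)²] = 0.61.
  - Fisher p = 0.15.
- Rank test: the pooled counts 4/14/6 have midranks 2.5, 11.5 and 21.5. The second arm's rank sum is 2(2.5) + 9(11.5) + 1(21.5) = 130, against 150 expected. The tie-corrected variance is (144/12) × [25 - 3000/(24 × 23)] = 234.8. So z = -20/15.3 = -1.31 and p = 0.19. The probability index is (130 - 78)/144 = 0.36.

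Neither finer test is significant. The gain is that the Grade 3 gap and its uncertainty are reported.

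**Step 3: probability of rejection when only Grade 3 changes.** Grade 2+ is held equal in both arms, and Grade 3 falls from 40% to the rate shown. Fisher is by exact enumeration and the rank test by simulation.

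| Grade 3 falls to | Fisher, Grade 2+ (85% / 70%) | Rank test (85% / 70%) | Fisher, Grade 3+ |
|---|---|---|---|
| 20% | 0.7% / 1.7% | 13% / 10% | 9% |
| 10% | 0.7% / 1.7% | 24% / 16% | 23% |
| 5% | 0.7% / 1.7% | 31% / 20% | 36% |

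The planned test stays at its own type I error. The two alternatives respond with low power, and neither is consistently better.

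**Step 4: a shift along the whole scale.** With a common odds ratio of 3, uncorrected chi-square on Grade 2+ (true size 2.9% to 6.4%) can be set against the rank test. This separates the cost of dichotomising from Fisher's conservatism (true size 0.7% to 2.3%).

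| Control Grade 2+ | Fisher | Chi-square | Rank |
|---|---|---|---|
| 85% | 9% | 18% | 28% |
| 70% | 16% | 29% | 29% |
| 50% | 14% | 26% | 28% |
| 30% | 7% | 16% | 24% |

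The loss from dichotomising runs from none (70%) to moderate (85% and 30%).

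**Step 5: the time point.** Section 11.2.3 treats the 1-month visit as after treatment, so the natural reading of 11.2.2 is the last RT-week visit. Section 6.4 continues assigned skin care until 1 month after RT, so the follow-up visit is a possible second reading. A third is any Grade 2+ by the end of treatment, which would use the weekly grades. Grades 2 and 3 are merged on all three.

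**The case against.** The strongest reply is that this is one of three components of one secondary objective, in a pilot whose primary outcome and sample size rest on compliance. The Grade 2+ threshold is defined in 5.2.2.1 and used consistently in 11.2.2. Every grade goes to REDCap, so nothing is lost. All of that stands, and it limits the weight of the point. It does not supply a planned clinician-graded result that reflects severity above Grade 2.

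The reply is also right about power. Step 3 uses the pattern least favourable to the planned test, and Step 4 shows that the loss can be nil. An ordinal test has no consistent advantage over a direct Grade 3+ comparison, so the Grade 3+ proportion belongs in the remedy.

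Three stronger readings are tempting, and the documents do not support them:
- **That severity is not analysed at all.** PRO-CTCAE and DLQI are compared as graded scores over time.
- **That 11.2.2 has no time point.** It names the end of treatment; only the link to a calendar visit is missing.
- **That Grade 2+ will sit at a ceiling.** Section 1.0 cites about 85% with moderate-to-severe reactions, and the Study Rationale about 30% with Grade 2 or worse. Neither rate is specific to head and neck cancer. The rationale says high-grade risk is higher in these patients but gives no rate.

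**Conclusion.** The point holds for the clinician-graded component. The objective is severity, the form records grade 0 to 5 at every visit, and the only planned analysis is Grade 2+ yes/no. On any reading of 11.2.2, a shift from Grade 3 to Grade 2 is invisible. That conclusion needs no assumed rates. The power figures and the worked example do rest on assumed grade distributions and serve as illustration only.

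The change is worth making because it costs little. It is not a flaw in the primary analysis. Low power at 12 per arm is not itself an error, since the plan claims none for this comparison. Tying the end of treatment to a visit is a minor clarification.

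**What to change.** In 11.2.2, mirrored in 5.2.2.1:
1. Keep the Grade 2+ Fisher comparison, state that it uses the last RT-week visit, and add the difference in proportions with a 95% CI. Say how a patient who leaves before that visit is counted.
2. Add a table by arm of CTCAE dermatitis grade 0 to 5 at that visit, with the Grade 3+ proportion and its between-arm difference with a 95% CI.
3. Add one exploratory ordinal comparison of grade at that visit, for example a Wilcoxon rank-sum test with the probability index and its 95% CI.
4. Optionally, describe worst grade through the 1-month visit by arm, with exits by arm beside it.

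Item 4 should stay descriptive because early leavers can be scored as mild. With no true effect and assumed grades 0/1/2/3 of 2/13/45/40%, scoring 2 of 12 patients in one arm as Grade 1 moves the rank test's size from about 5% to 7%. Scoring 3 of 12 that way moves it to about 11.5%.

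The cost is wording only, since the Appendix H grades already go to REDCap (section 10.0). The downside is one or two extra exploratory comparisons with low power at 12 per arm. The primary analysis is unchanged.

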7.0 Study Assessments

7.1 Study Assessment Visits

7.1.1 Baseline Visit

After informed consent, registration and randomization, study staff will collect baseline demographic information. This includes information such as age, gender, race/ethnicity, medical history, current medications, allergy history. The skin within the region of

interest will be photographed. Study personnel will collect a baseline skin toxicity assessment (Appendix H). Subjects will complete the Dermatology Life Quality Index (Appendix I).

The baseline assessment may occur at any time between registration and the first radiation treatment. A convenient visit may include the radiation treatment planning CT simulation, which occurs in the Department of Radiation Oncology approximately 1.5-2 weeks prior to the start of RT. At this visit, patients may be approached for the baseline assessment. This will be coordinated by study staff.

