7.2 Study Calendar

	Prior to RT Start	Weekly During RT ^a	1-month Follow- up Visit
Informed consent	Χ		
Demographics (Appendix B, C, D)	X		
Medical history (Appendix E)	X		
Medications (Appendix F)	Χ		
Compliance & Tolerability Assessment (Appendix G)	Х	Х	Х
Toxicity Assessment Form (Appendix H)	Х	X	Х
Dermatology Life Quality Index (Appendix I)	Х	X	Х
Photographic Documentation of the Skin in the Region of Interest	Х	Х	Х

^a Assessments may occur within +/- 5 days of weekly on-treatment visit. On-treatment visits occur weekly until patient has completed (or stopped) treatment. If treatment breaks are necessary, patient may be seen on weeks 8 or 9 if needed.

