b. In the last 7 days, how much did MOUTH OR THROAT SORES INTERFERE with your usual or daily activities?							
O Not at all	O A little bit	O Somewhat	O Quite a bit	O Very much			

Appendix I – Dermatology Life Quality Index Study Number: PID: PI: Date (mm/dd/yy): ___ / ___/ ___/ To be completed by the patient. The aim of this questionnaire is to measure how much your skin problem has affected your life OVER THE LAST WEEK. Please tick (✓) one box for each question. 1. Over the last week, how itchy, sore, painful or stinging Very much has your skin been? A lot A little Not at all Over the last week, how embarrassed or self conscious Very much have you been because of your skin? A lot A little Not at all 3. Over the last week, how much has your skin interfered with Very much you going shopping or looking after your home or garden? A lot A little Not at all Not relevant 4. Over the last week, how much has your skin influenced the Very much clothes you wear? A lot A little Not at all Not relevant 5. Over the last week, how much has your skin affected any Very much social or leisure activities? A lot A little Not at all Not relevant 6. Over the last week, how much has your skin made it difficult Very much for you to do any sport? A lot A little Not at all Not relevant 7. Over the last week, has your skin prevented you from Yes working or studying? Not relevant No If "No", over the last week how much has your skin been a A lot problem at work or studying? A little Not at all Very much 8. Over the last week, how much has your skin created problems with your partner or any of your close friends or A lot relatives? A little Not at all Not relevant Over the last week, how much has your skin caused any Very much sexual difficulties? A lot A little Not at all Not relevant 10. Over the last week, how much of a problem has the Very much treatment for your skin been, for example by making your A lot A little home messy, or by taking up time? Not at all Not relevant Please check you have answered EVERY question. Thank you. To be completed by research nurse: Score:

Protocol version date 12/10/21 Page **38** of **55**

DERMATOLOGY LIFE QUALITY INDEX (DLQI) - INSTRUCTIONS FOR USE

The Dermatology Life Quality Index questionnaire is designed for use in adults, i.e. patients over the age of 16. It is self explanatory and can be simply handed to the patient who is asked to fill it in without the need for detailed explanation. It is usually completed in one or two minutes.

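### The repeated-measures models in 11.2.3 and 11.2.4 make no use of baseline scores, do not say how series of different length are handled, and name no contrast for the DLQI comparison at each visit

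*Combined protocol and SAP*

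**What the plan says.** - **Model.** For PRO-CTCAE, 11.2.3 compares mean scores "using a simple repeated measures analysis of variance model with treatment group as the independent variable of interest". Section 11.2.4 repeats this model for the DLQI, with treatment group as the key variable. Section 11 gives no further terms, covariance structure or missing-data rule for these outcomes.
- **Visits analysed.** The PRO-CTCAE scores are those "collected each week over the 6-7 weeks of radiation therapy", plus the one-month follow-up; baseline is not in the list. For the DLQI, "Mean DLQI score at each time point will be compared between the KeraStat and RSC groups", without saying whether baseline is one of those time points.
- **Baseline data.** Section 7.1.1 and the calendar in 7.2 have Appendix H (which holds the PRO-CTCAE items) and the DLQI completed before radiotherapy starts.
- **Series length.** Per 7.2, "On-treatment visits occur weekly until patient has completed (or stopped) treatment", and "If treatment breaks are necessary, patient may be seen on weeks 8 or 9 if needed". Section 6.6 lists stopping of radiotherapy as a reason for removal from the study.

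**The concern.** Three things are left open. First, baseline scores exist for both instruments but have no stated role, so a possible gain in precision is unused. For the DLQI it is also unclear whether baseline enters as an outcome visit. Second, a classical repeated-measures ANOVA expects the same complete set of visits from everyone, which this schedule does not produce. Third, a group effect alone is one difference averaged over visits, whereas 11.2.4 promises a comparison at each visit.

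Section 2.2.2 makes these two of the three evaluations of effectiveness, and the Study Rationale in section 1.0 says the data are to inform later randomised comparative studies. Two competent analysts following the present text could use different visits, patients and baseline handling, and so carry different estimates forward.

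**Working it through.** **1. The plan's own figure.** The only precision figure is in 11.3: a maximum 95% interval width of 0.578 for compliance with 12 per arm. The exact (Clopper-Pearson) interval for 6 of 12 is 0.2109 to 0.7891, width 0.578, so it reproduces. It concerns the primary outcome and is not affected. No figure is given for 11.2.3 or 11.2.4.

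**2. Visits per patient (from the documents).** PRO-CTCAE: 6 + 1 = 7 for a six-week course and 7 + 1 = 8 for a seven-week course. DLQI: up to 9 + 1 = 10 if weeks 8 and 9 are used. Series are unequal even with perfect attendance. A strictly balanced layout would have to leave out either week 7 or every six-week patient.

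**3. Baseline as an outcome visit (DLQI).** If baseline were one of the averaged visits, a constant post-baseline effect would shrink to 7/8 = 0.875 of its size (7 post-baseline visits) or 8/9 = 0.889 (8 visits).

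**4. Complete series only (assumed miss rates).** If all 8 visits were required, the share kept with independent misses at rate q is (1 - q)^8. The clustered column uses a beta-binomial with intra-patient correlation 0.3.

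| Miss rate per visit | Independent, of 24 | Clustered, of 24 |
|---|---|---|
| 2% | 0.851, 20.4 | 0.925, 22.2 |
| 5% | 0.663, 15.9 | 0.821, 19.7 |
| 10% | 0.430, 10.3 | 0.669, 16.1 |

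**5. Baseline as covariate (assumed correlations).** Take the mean of the 7 visits common to all full courses (weeks 1-6 and the 1-month visit), with correlation r between post-baseline visits and r0 between baseline and each of them. The variance of a patient's mean, in SD² units, is V = (1 + 6r)/7. The adjusted-to-unadjusted variance ratio is [1 + 1/(24 - 4)] × (1 - r0²/V); the first factor, 1.05, is the cost of estimating the slope with 12 per arm.

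| | V | r0 = 0.1 | r0 = 0.3 | r0 = 0.5 |
|---|---|---|---|---|
| r = 0.3 | 0.400 | 1.024 | 0.814 | 0.394 |
| r = 0.5 | 0.571 | 1.032 | 0.885 | 0.591 |
| r = 0.7 | 0.743 | 1.036 | 0.923 | 0.697 |
| Single visit | 1 | 1.040 | 0.956 | 0.788 |

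Adjustment breaks even at r0 = sqrt(V × (1 - 1/1.05)), which is 0.165 for the average (r = 0.5) and 0.218 for a single visit.

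**6. Precision at one visit.** The unadjusted 95% half-width with 12 per arm is t(22) × sqrt(2/12) = 2.074 × 0.408 = 0.85 SD.

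**The case against.** The strongest reply is that nothing here is shown to be wrong. Calling treatment the variable of interest, or the key one, does not exclude others; a repeated-measures ANOVA ordinarily carries a visit factor and can carry an interaction; and the term does not rule out a likelihood fit that uses every visit. Randomisation makes the unadjusted comparison valid. Section 3.2 excludes prior radiotherapy to the area, medically necessary topical steroids there, and active scleroderma or lupus on systemic medication. Pre-radiotherapy skin scores near the floor are therefore plausible, and adjustment might then gain nothing. Assessments are attached to routine weekly visits with a window of 5 days either side, so few may be missed. The 24 patients in step 4 are already the number left after attrition from 28, so that table may count some loss twice.

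All of this stands, and it limits the point. A reader might infer that the plan will discard patients with incomplete series and lose a third or more of the sample. The documents do not support that: complete-case deletion is a risk of one classical implementation, not a stated rule, and the miss rates are assumed. What survives is that the text does not settle which visits count, what baseline does, or how the promised per-visit DLQI differences are obtained.

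**Conclusion.** The concern holds as a minor one. Three facts come directly from the documents: series length differs by design, baseline scores are collected without a stated analysis role, and the per-visit DLQI comparison lacks the contrasts it needs. A mixed model would serve better with data already planned, and adjusting for baseline is a cheap addition.

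It would go too far to read this as an invalid treatment comparison or an under-sized trial. The unadjusted comparison is sound, these are secondary outcomes of a pilot, and the compliance analysis and its interval width do not change. The patient counts and variance ratios illustrate assumed miss rates and correlations and are not expected effects. The gain from baseline could be large, small or slightly negative.

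**What to change.** In 11.2.3 and the first sentence of 11.2.4, replace the model with the following. Leave the t-test on the highest DLQI score as it is.

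- **Model:** a REML linear mixed model on all available post-baseline visits, with fixed effects for group, visit and group-by-visit, a random patient intercept (compound symmetry) and small-sample degrees of freedom. The structure should be stated: an unstructured matrix over 8 visits has 8 × 9/2 = 36 parameters, against 24 patients.
- **Missed or unscheduled visits:** no row is contributed, and the patient stays in.
- **Visits:** each week keeps its own level, with no pooling and no last-value rule. The averaged difference is taken over weeks 1-6 and the 1-month follow-up, which all full courses share. Week 7 and later are summarised descriptively. Six-week patients have no such rows, and weeks 8-9 follow treatment breaks, which section 1.0 says severe skin reactions can cause, so presence there may depend on the outcome.
- **Baseline:** a covariate for the DLQI and for the PRO-CTCAE dryness, itching and mouth or throat sore items, but not for the radiation-skin-reaction item, which has no meaningful pre-radiotherapy value. Baseline is not an outcome visit.
- **Reporting:** the averaged difference with its 95% interval and, for the DLQI, per-visit differences with 95% intervals labelled descriptive.

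The cost is analysis wording only. The model assumes data are missing at random. Compound symmetry assumes equal variance at every visit, on which the per-visit intervals lean. Variance rises by about 3-4% if baseline is nearly uncorrelated with outcome (0.1) or near the floor. Per-visit intervals stay wide, at about ±0.85 SD unadjusted.
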